8.3 Adverse reactions with TRC105

The most common adverse events associated with TRC105 are infusion reactions that are successfully mitigated with premedications and prolongation of the infusion time, hemorrhages (mostly grade 1 and 2), headaches, and hypoproliferative anemia.

8.3.1 Hypoproliferative Anemia

TRC105 was administered to 50 patients as part of a phase 1 first-in-human study of solid tumors. Dose escalation proceeded stepwise, and the majority of adverse events were grade 1 or 2. The MTD was 10 mg/kg weekly, and 15 mg/kg every two weeks was also well tolerated. At 15 mg/kg weekly, all 3 patients that remained on study through cycle 2 developed dose-limiting grade 3 anemia, and one of the three progressed to grade 4 anemia by cycle 3. In all three patients, the anemia resolved following discontinuation of treatment. Anemia has been observed in other trials of TRC105.

The dose-limiting anemia at 15 mg/kg weekly was associated with accumulation of TRC105 and characterized by a low reticulocyte production index. Additional laboratory and clinical evaluations excluded common causes of anemia including blood loss, hemolysis, plasma volume expansion, inadequate erythropoietin, iron deficiency, and vitamin B-12 or folate deficiency. Bone marrow aspiration attempts in the patient with grade 4 anemia yielded insufficient material to permit evaluation of the cause of anemia.

The hypoproliferative anemia was believed to result from TRC105-mediated suppression of proerythroblasts, the only cells in the marrow known to express substantial levels of CD105. Anemia was manageable with standard supportive measures including erythropoietin and packed red blood cell transfusion. One patient dosed in study 105ST101 required dose reduction from 10 mg/kg to 7.5 mg/kg weekly for grade 3 anemia at month 12 and further dose reduced to 6 mg/kg and continued treatment with a minor radiographic response for 20 months. All patients receiving TRC105 should be monitored for anemia and treated appropriately (including possible TRC105 dose reduction).

depletion, is a known adverse event that occurs in <1% of patients receiving therapeutic proteins like monoclonal antibodies. The risk of syncope can be minimized by encouraging patient hydration prior to the initial treatment with TRC105 and avoiding the treatment of patients who are volume depleted.

Hypersensitivity reactions to therapeutic protein infusions are a potential risk for sensitized patients, and TRC105 should be avoided or used with caution in patients with known hypersensitivity to any component of the drug product.

8.3.4. Other Potential Risks

Low grade fatigue is a commonly reported adverse event attributable to TRC105 although its cause is unclear and appears not to be caused by thyroid dysfunction. Headaches (grade 1 to 3) have been observed following TRC105 treatment, generally within hours following completion of the initial infusion. Headaches are throbbing in nature, have not been associated with radiographic abnormalities, and have responded to treatment with non-steroidal anti-inflammatory agents and to

triptans. Headaches were particularly prominent in patients treated with TRC105 in combination with bevacizumab. Headaches were more common and most severe when TRC105 and bevacizumab were initially dosed on the same day and were ameliorated when the first dose of TRC105 was dosed one week following bevacizumab and was given over two days. Nasal congestion and periorbital edema have been observed with TRC105 dosing, particularly when dosed in combination with bevacizumab. The edema has been transient in nature and treated with corticosteroids. Antihistamines are useful for nasal congestion.

Flushing and rash (typically maculo-papular and erythematous) occasionally develop following infusion of TRC105. Low grade anorexia, nausea, and vomiting are seen infrequently. Isolated serious adverse reactions include grade 2 pancreatitis in a hepatocellular carcinoma patient in treated with TRC105 in combination with sorafenib and grade 3 infected skin lipoma/cyst observed in a phase 2 study of TRC105 as a single agent in patients with metastatic bladder cancer. Both resolved without sequelae.

While thrombosis has not been frequent on TRC105 treatment, patients who develop arterial thrombosis or grade 3 or 4 venous thrombosis should discontinue TRC105 therapy. Those with uncomplicated grade 1 or 2 venous thrombosis and with normal platelet count and platelet function, who appear to be benefiting from TRC105 therapy, may be anticoagulated and continue on TRC105 therapy at the discretion of the investigator. Patients with coagulation parameters above standard therapeutic levels (e.g., INR > 3) are at increased risk of hemorrhage and should therefore not receive TRC105.

Transient Grade 3 hepatic encephalopathy occurred in one patient with cirrhosis and hepatocellular carcinoma who received TRC105 in combination with sorafenib.

A patient with glioblastoma developed temporary confusion and slurred speech following treatment with TRC105 and bevacizumab that required hospitalization for observation. Another patient with glioblastoma, who underwent resection and had a history of an abnormal collection of cerebral spinal fluid, developed a grade 2 cerebral spinal fluid leak.

Grade 3 myocardial infarction (non-Q wave infarct associated with hypertension following an infusion reaction) was observed in a patient with hepatocellular cancer following treatment with TRC105 that resolved without sequelae. In addition, a Grade 5 myocardial infarction occurred in a patient with coronary artery disease who received TRC105 in combination with sorafenib. Patients with evidence of active coronary artery disease are excluded from participation in this trial (see exclusion criteria).

Adult respiratory distress syndrome that required temporary intubation occurred in one patient who received TRC105 with pazopanib, from which the patient recovered. Of note, interstitial lung disease has been added as an adverse drug reaction and warning/precaution to the core safety information for pazopanib.

Infections have been observed rarely. Grade 3 infected lipoma/cyst was observed in a Phase 2 study of TRC105 as a single agent in patients with metastatic bladder cancer. Grade 3 orbital cellulitis and grade 3 brain abscess were observed in patients treated with TRC105 and bevacizumab and

considered possibly related to TRC105. Grade 1 and 2 gingivitis including infection and ulceration has also been observed. Overall, infections have been observed in fewer than 5% of patients and have largely been considered unrelated to treatment with TRC105.

9. DATA COLLECTION AND STUDY MANAGEMENT

The study must be conducted as described in this approved protocol. Should amendments to the protocol be required, the amendments will be originated and documented by the Principal Investigator at UAB. The written amendment will be sent to the IRB at the investigator's site for approval. All revisions to the protocol will be provided to Novartis and TRACON by UAB. The Investigator should not implement any deviation or change to the protocol without prior review and documented approval/favorable opinion from the IRB of an Amendment, except where necessary to eliminate an immediate hazard(s) to study patients. Documentation of approval signed by the chairperson or designee of the IRB(s) must be sent to the UAB Clinical Protocols and Data manager Shared Facility Regulatory Office ([name] fax 205-). If the revision is an Administrative Letter, Investigator must inform their IRB(s)/IEC(s).

Principal investigator will hold the IND for the trial. All patients must be registered with the Clinical Trials Network and Monitoring Office of the UAB Comprehensive Cancer Center ([name], O.C.N.) before enrollment in study. Prior to initiation of therapy eligibility criteria must be confirmed. At the time of registration, a study identification number will be generated. All subsequent case report forms will use this study identification number.

9.1 Data Collection

The study will have electronic CRF in OnCore for each subject (UAB CCC). Entries made in the CRF must be verifiable against source documents; any discrepancies should be explained and documented. The investigator will be responsible for reviewing all data and CRF entries and will sign and date the designated pages in each subject's CRF, verifying that the information is true and correct. The investigator is responsible for the review and approval of all responses. Patients will be registered in the Clinical trial Network and Monitoring office of the UAB Comprehensive Cancer Center. **9.2 Data Management**

Data management will be performed from CRFs. All CRF data will be entered into a validated database. All data entry, verification, and validation will be performed in accordance with the current standard operating procedures of the Clinical Trials and Data Management Shared Facility of the UAB CCC. The database will be authorized for lock once all defined procedures are completed.

9.3 Study Management

9.3.1 Institutional Review Board Approval and Informed Consent

Before study initiation, the Investigator must have written and dated approval/favorable opinion from the IRB for the protocol, consent form, patient recruitment materials/process (e.g., advertisements), and any other written information to be provided to patients. The Investigator should provide the IRB with reports, updates, and other information (e.g., Safety Updates, Amendments, Administrative

Letters) according to regulatory requirements or Institution procedures. Copies of the initial IRB approval as well as annual re-approvals must be submitted to UAB. UAB will provide copies of IRB approval to Novartis and TRACON.

It is expected that the IRB will have the proper representation and function in accordance with federally mandated regulations. In obtaining and documenting informed consent, the investigator should comply with the applicable regulatory requirement(s), and should adhere to Good Clinical Practice (GCP) and to ethical principles that have their origin in the Declaration of Helsinki. Before recruitment and enrollment onto this study, the patient will be given a full explanation of the study and will be given the opportunity to review the consent form. Each consent form must include all the relevant elements currently required by the FDA Regulations and local or state regulations. Once this essential information has been provided to the patient and the investigator is assured that the patient understands the implications of participating in the study, the patient will be asked to give consent to participate in the study by signing an IRB-approved consent form.

Prior to a patient's participation in the trial, the written informed consent form should be signed and personally dated by the patient or the patient's legally acceptable representative, and by the person who conducted the informed consent discussion. Documentation of IRB approval must be on file before any patient can be registered. Registration begins with signed informed consent.

9.3.2 Data confidentiality

Information about study subjects will be kept confidential and managed under applicable laws and regulations. Those regulations require a signed subject authorization informing the subject of the following:

- What protected health information (PHI) will be collected from subjects in this study
- Who will have access to that information and why
- Who will use or disclose that information
- The rights of a research subject to revoke their authorization for use of their PHI.

In the event that a subject revokes authorization to collect or use PHI, the investigator, by regulation, retains the ability to use all information collected prior to the revocation of subject authorization. For subjects that have revoked authorization to collect or use PHI, attempts should be made to obtain permission to collect follow-up safety information (e.g. has the subject experienced any new or worsened AEs) at the end of their scheduled study period. The data collection system for this study uses built-in security features to encrypt all data for transmission in both directions, preventing unauthorized access to confidential participant information. Access to the system will be controlled by a sequence of individually assigned user identification codes and passwords, made available only to authorized personnel who have completed prerequisite training.

9.3.3 Study Monitoring

Data will be captured on electronic CRFs, and supporting documents will be faxed to the UAB Clinical Trials Network and Monitoring Office. Personnel from the Clinical Trials Network and Monitoring office of the University of Alabama at Birmingham will monitor the trial in real time and will periodically visit the investigative site to ensure proper conduct of the trial and proper collection

of the data.

The principal investigator will check the completeness of patient records, the accuracy of entries on the CRFs, the adherence to the protocol to Good Clinical Practice, the progress of enrollment, and to ensure that study treatment is being stored, dispensed, and accounted for according to specifications. Key study personnel must be available to assist the principal investigator in these periodic checks.

The investigator must maintain source documents for each patient in the study, consisting of case and visit notes (hospital or clinic medical records) containing demographic and medical information, laboratory data, and the results of any other tests or assessments. All information recorded on CRFs must be traceable to source documents in the patient's file. The investigator must also keep the original signed informed consent form (a signed copy is given to the patient).

Trial will be followed by the Clinical Trials Monitoring Committee and audited by the UAB CCC according to the institutional guidelines.

9.3.4 Record Retention

Study documentation includes all Case Report Forms, data correction forms or queries, source documents, Sponsor-Investigator correspondence, monitoring logs/letters, and regulatory documents (e.g., protocol and amendments, IRB correspondence and approved signed patient consent forms). Source documents include all recordings of observations or notations of clinical activities and all reports and records necessary for the evaluation and conduction of the clinical research study. Government agency regulations and directives require that all study documentation pertaining to the conduct of a clinical trial must be retained by the study investigator. In the case of a study with a drug pursuing regulatory approval and marketing, these documents shall be retained for at least two years after the last approval of marketing application in an International Conference on Harmonization (ICH) region. In all other cases, study documents should be kept on file until three years after the completion and final study report of this investigational study.

If the Investigator withdraws from the study (e.g., relocation, retirement), the records shall be transferred to a mutually agreed upon designee (e.g., another Investigator, IRB). Notice of such transfer will be given in writing to NOVARTIS and TRACON Pharmaceuticals. Records of the patient's participation in this study will be kept confidential so far as permitted by law. However, the patient's doctor and his/her staff, representatives of NOVARTIS and TRACON Pharmaceuticals, representatives of the U.S. Food and Drug Administration, and the IRB will be able to inspect patient records and have access to confidential information which identifies the patient by name. Any publication of data will not identify the patient by name. Should the patient's medical record need to be reviewed by a foreign regulatory agency, a member of the IRB staff will observe the review so that the record is not removed, copied, or identifiable information recorded in any manner.

9.3.5 Obligations of Investigators

The Principal Investigator is responsible for the conduct of the clinical trial at the site in accordance with Title 21 of the Code of Federal Regulations and/or the Declaration of Helsinki. The Principal Investigator is responsible for personally overseeing the treatment of all study patients. The Principal Investigator must ensure that all study site personnel, including sub-investigators and other study

staff members, adhere to the study protocol and all FDA/GCP/NCI regulations and guidelines regarding clinical trials both during and after study completion.

The Principal Investigator at each institution or site will be responsible for ensuring that all the required data will be collected and entered onto the Case Report Forms. Periodically, monitoring visits will be conducted and the Principal Investigator will provide access to his/her original records to permit verification of proper data entry. At the completion of the study, all case report forms will be reviewed by the Principal Investigator and will require his/her final signature to verify the accuracy of the data.

10. STATISTICAL CONSIDERATIONS

This is a phase I/II study with the primary objective to characterize the tolerability and feasibility of a novel combination of agents. The Primary Endpoint is defined as the determination of MTD and RP2D and rates of treatment-related toxicities. The secondary efficacy endpoints are rates of pCR or down-staging. The principal investigator will hold the IND for the trial (Appendix F).

10.1 Sample Size and Power Justification

A. The dose escalation part of the study will follow a conventional 3+3 dose escalation design according to the schema above. We anticipate that up to 18 patients will be enrolled in this part anticipating that dose level 1 or 2 will be the RP2D. The number of patients to be enrolled ranges from 3 (if $\geq 2/3$ DLTs in cohort 1) to 18 (if enrollment of 6 patients in all cohorts).

B. The sample size of 20 in Phase II part study is NOT determined by the statistical power but the feasibility and relative precision of estimate, e.g. standards error of the estimation is $\leq 10\%$. We will estimate the pCR of the combination to generate hypotheses for further clinical investigations. In order to minimize exposure of patients to ineffective therapy, Gehan’s two-stage design will be used⁵¹ which allows for the rapid rejection of an ineffective treatment at the end of the first stage, and provides an estimation of the success rate with a given precision, at the end of the second stage. The study will enroll 10 patients first, and if no patient has pCR or downstaging, it is unlikely ($p=0.1074$) that 0/10 responses would occur if the true response rate were $>20\%$. If responses were 0/10, the phase II portion will be closed. If at least one patient has pCR or downstaging, an additional 10 patients will be treated (total of 20). With an accrual of 20 patients to phase II portion of the study, estimated two-sided 95% confidence intervals (CI) would be 1.2%-31.7%, 5.7% -43.6% and 11.8%-54.3% if pCR is 10%, 20% or 30% respectively. The confidence intervals are calculated using the exact method Clopper-Pearson intervals⁵⁴.

Table 10-1 shows the probability of early termination and observing one response or at least one response at the first stage ($N_1=10$).

Table 10.1: Probability of early termination and observing one response or at least one response at the first stage ($N_1=10$)

True ORR	Probability of having zero response ($x=0$)	Probability of having one response ($x=1$)	Probability of having at least one response ($x\geq 1$)
----------	---	--	---

0.1	0.3486	0.3874	0.6513
0.2	0.1074	0.2684	0.8926
0.30	0.0282	0.1211	0.9718

10.2 Statistical Analysis

The primary analysis is of safety and will include any patients who receive at least one dose of the investigational regimen. The rate of adverse events will be estimated at the end of the study along with two-sided 95% exact CIs (Clopper-Pearson intervals). At the completion of the study, the secondary endpoint of pCR or downstaging rate will be estimated along with two-sided 95% CIs with the exact method of Clopper-Pearson intervals. Secondary endpoint analysis will be descriptive. Mean, median, geometric mean, range and coefficient of variation will be used to describe continuous demographic variables. Frequency and proportion will be used to describe categorical variables.

We will use descriptive statistics (mean, median, geometric mean, coefficient of variation, and 95% confidence intervals) and graphical displays (mean concentration-time graphs, scatter plots, box plots or spaghetti plots) to evaluate the pharmacokinetic parameters of the TRC105 and everolimus. We will use descriptive statistics (mean, median, geometric mean, coefficient of variation, and 95% confidence intervals) and graphical displays (scatter plots, box plots, plots of PD parameters against PK data) to analyze the changes in markers of proliferation and angiogenesis with the investigational treatment.

Exploratory analysis will be conducted on the correlations between clinical outcomes and pharmacodynamic biomarkers or translation profiles. Translational profiles will be analyzed between responders and non-responders and the differences between responders and non-responders will be presented in scatter plots along with corresponding 95% CI. Quartile normalization and logarithmic transformation will be conducted before analysis. Logistic regression analysis will be used to predict response with translational profiles or biomarkers with or without adjustment for covariates, e.g. age. Multivariate Cox proportional hazards model will be used to identify a set of biomarkers for prediction of response. Odds ratios with 95% CIs will be calculated for each significant biomarker in terms of predicting response. However, it is recognized that sample size may be too small for such analyses and these analyses are conducted only to generate hypotheses that will require further validation.

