(a) Sample size justification: The dose escalation part of the study will follow a conventional 3+3 dose escalation design according to the schema above. Up to 18 patients will be enrolled in this part anticipating that dose level 1 or 2 will be the RP2D. The number of patients to be enrolled ranges from 3 ($\geq 2/3$ DLTs in cohort 1) to 18 (enrollment of 6 patients in all cohorts). The sample size of 20 in Phase II part study is NOT determined by the statistical power but the feasibility and relative precision of estimate, e.g. standard error of the estimation is $\leq 10\%$. We will estimate the pCR of the combination to generate hypotheses for further clinical investigations. A Gehan's two-stage design will be used⁵¹ which allows for the rapid rejection of an ineffective treatment at the end of the first stage, and provides an estimation of the success rate with a given precision, at the end of the second stage. The study will enroll 10 patients first. If no patient has pCR or downstaging, it is unlikely ($p=0.1074$) that 0/10 responses would occur if the true response rate were $>20\%$ and the phase II portion will be closed. If at least one patient has pCR or downstaging, an additional 10 patients will be treated (total of 20). With an accrual of 20 patients to phase II portion of the study, estimated two-sided 95% confidence intervals (CI) would be 1.2%-31.7%, 5.7% -43.6% and 11.8%-54.3% if pCR is 10%, 20% or 30% respectively. The confidence intervals are calculated using the exact method Clopper-Pearson intervals⁵⁴. Final analysis will include all patients enrolled in the trial.

(b) Analytic plan for primary objective: The rate of adverse events will be estimated at the end of the study along with two-sided 95% exact CIs (Clopper-Pearson intervals).

(c) Analytic plan for secondary objectives:

1. pCR or downstaging rate will be estimated along with two-sided 95% CIs with the exact method of Clopper-Pearson intervals.
2. We will use descriptive statistics (mean, median, geometric mean, coefficient of variation, and 95% confidence intervals) and graphical displays to evaluate the pharmacokinetic parameters of the TRC105 and everolimus.
3. We will use descriptive statistics (mean, median, geometric mean, coefficient of variation, and 95% confidence intervals) and graphical displays to analyze the changes in markers of proliferation and angiogenesis with the investigational treatment.

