1. OBJECTIVES AND ENDPOINTS

1.1 Objectives

1.1.1 Primary Objective

Determine the tolerability and feasibility of combining everolimus and TRC105 with letrozole administered for 24 weeks in the preoperative (neoadjuvant) setting in postmenopausal women with newly diagnosed potentially resectable local or locally advanced (T2-T4a-c, N0-2, M0; excluding patients with T4d or inflammatory breast cancer) estrogen and/or progesterone receptor positive, Her2/neu negative breast cancer.

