1.2 Endpoints

1.2.1 Primary Endpoint

Determine the maximum tolerated dose (MTD), the recommended phase 2 dose (RP2D) and rates of adverse events associated with the combination of letrozole with everolimus and TRC105.

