7.2.2 Definitions

Evaluable for toxicity. All patients who receive at least one dose of any or all of the drugs of the investigational regimen will be evaluable for toxicity from the time of their first treatment until discontinuation or completion of the investigational therapy.

Evaluable for objective response. Only those patients who have measurable disease present at baseline, have received at least one cycle of therapy, and have had their disease re-evaluated will be considered evaluable for response. These patients will have their response classified according to the definitions stated below.

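### The primary adverse-event rate is planned over everyone dosed, across up to three dose levels, and no estimate at the RP2D is specified

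*Combined protocol and SAP*

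**What the plan says.** The primary objective (1.1.1) is to "Determine the tolerability and feasibility of combining everolimus and TRC105 with letrozole administered for 24 weeks in the preoperative (neoadjuvant) setting". The primary endpoint (1.2.1) is to "Determine the maximum tolerated dose (MTD), the recommended phase 2 dose (RP2D) and rates of adverse events associated with the combination" of the three drugs.

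The analysis set is everyone dosed. Section 10.2 says "The primary analysis is of safety and will include any patients who receive at least one dose of the investigational regimen", and then "The rate of adverse events will be estimated at the end of the study along with two-sided 95% exact CIs (Clopper-Pearson intervals"). Section 7.2.2 agrees: "All patients who receive at least one dose of any or all of the drugs of the investigational regimen will be evaluable for toxicity". The synopsis (Statistical Methods, a) is broader still: "Final analysis will include all patients enrolled in the trial".

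Table 4-1 lists three combinations of TRC105 (mg/kg every 2 weeks) and everolimus (mg daily): cohort 1 at 15/5, cohort 2 at 15/10 and cohort -1 at 10/5. Section 10.1 puts the phase I maximum at "18 (if enrollment of 6 patients in all cohorts"). Phase II adds up to 20 patients at the RP2D (4.1.3, 4.2).

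The factors for later subgroup analysis in 10.3 are grade, stage, nodal status and age. Dose level and study phase are not among them. The only safety quantity tied to a dose level is the count of first-cycle dose-limiting toxicities (DLTs) in 4.1.1 to 4.1.3, which selects the MTD and RP2D.

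**The concern.** A follow-on trial would need the adverse-event rate over the full preoperative course at the dose carried forward. The plan does not commit to producing that number. Its stated set joins RP2D patients with patients assigned other regimens, and the exact interval then refers to that mix.

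The protocol itself gives reasons to expect toxicity to vary with dose. Section 4.4 starts everolimus at the lower level because the higher one was linked to more adverse events in an earlier trial and might not be sustainable for six months. The same section worries that the lower TRC105 dose leaves gaps in serum levels and so a risk of infusion reactions at each administration. A non-RP2D cohort could therefore be milder for some events and worse for others, and the distortion can go either way.

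The DLT rule does not fill the gap. It covers the first 4-week cycle of a 24-week course, in at most six evaluable patients per level. If the denominator is not fixed in advance, it may be chosen after the events are known.

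**Working it through.** **Inputs.** Cohorts of 3 or 6 (Table 4-2); up to three levels (Table 4-1); 20 patients in a full phase II (4.2); total enrolment of 26 to 38 (4.3). The gap in adverse-event rate between levels is an assumption, because the documents give none for this combination.

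**The plan's own figure.** Minimum: 3 + 3 + 20 = 26. Maximum: 6 + 6 + 6 + 20 = 38. Both reproduce.

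**How many levels open.** Under 4.1, clearing cohort 1 leads to cohort 2, and failing it leads to cohort -1. A route to phase II therefore normally opens two levels. Three levels need cohort 1 cleared, cohort 2 not tolerated, and cohort 1 then found not tolerated on return.

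**Formula.** All-treated rate minus RP2D rate = (n_other / N) × (p_other − p_RP2D).

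**Shares and shifts with a full phase II.** The RP2D column is the phase I RP2D cohort plus 20.

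| Route | At RP2D | At other doses | N | Share at other doses | Shift for a 20-point gap |
|---|---|---|---|---|---|
| Two levels: other 3, RP2D cohort 6 | 26 | 3 | 29 | 10.3% | 2.1 |
| Two levels: other 3, RP2D cohort 3 | 23 | 3 | 26 | 11.5% | 2.3 |
| Two levels: other 6, RP2D cohort 6 | 26 | 6 | 32 | 18.8% | 3.8 |
| Two levels: other 6, RP2D cohort 3 | 23 | 6 | 29 | 20.7% | 4.1 |
| Three levels: others 6 + 6, RP2D cohort 6 | 26 | 12 | 38 | 31.6% | 6.3 |
| Three levels: others 6 + 6, RP2D cohort 3 | 23 | 12 | 35 | 34.3% | 6.9 |

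Shifts are in percentage points. The sign is positive if the other doses are more toxic and negative if they are milder. For a 30-point gap, two levels give 3/29 × 30 = 3.1 to 6/29 × 30 = 6.2 points, and three levels give up to 12/35 × 30 = 10.3.

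If phase II stops after its first 10 patients, the share rises. With 18 in phase I it is 12/28 = 43%, and a 20-point gap shifts the rate by 8.6 points. Patients dosed and then replaced under 4.1.3 would also enter the set and are not counted here.

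**Illustration (assumed counts, three levels).** Suppose 5 of 26 patients at the RP2D and 6 of 12 at other doses have the event. The RP2D rate is 5/26 = 19.2% (exact 95% CI 6.6% to 39.4%). The all-treated rate is 11/38 = 28.9% (15.4% to 45.9%).

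**Check on the remedy.** The phase I RP2D cohort is selected for 0/3 or 1/6 DLTs (4.1.3). Assume a true first-cycle DLT rate of 25%, so that 20 phase II patients yield 5 expected events. Adding 0/3 gives 5/23 = 21.7%, and adding 1/6 gives 6/26 = 23.1%. These are 3.3 and 1.9 points too low for DLT-type events, similar in size to the two-level shift above. Phase II alone is free of this selection.

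**The case against.** The strongest reply is that 10.2 names a set and an interval type but never says that only one overall rate will be reported. A reader might infer that a single combined figure is prescribed and a split by cohort excluded. The text does not say so, and analysts may well tabulate by cohort. What remains is that nothing commits them to it.

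The endpoint wording also matters. A reader might infer that 1.2.1 asks for adverse-event rates at the RP2D specifically. It does not: it lists the MTD, the RP2D and adverse-event rates for the combination. An all-treated rate answers that wording, so it would also be too strong to say the interval has no target population. Its population is the treated mix. That mix is simply not the one a later trial would use.

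Safety at each dose is not ignored. DLTs are counted by level and determine the RP2D, 4.2 continues safety evaluation in phase II, and no decision or test depends on the all-treated interval. This limits the harm to reporting, but it supplies no 24-week rate at the RP2D.

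The size is modest. Section 10.1 anticipates cohort 1 or 2 as the RP2D, so the three-level figures are a corner case. Even the larger shifts are small beside an interval such as 6.6% to 39.4%. That is correct. Still, the shift is a bias, and naming the denominator in advance removes it.

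Finally, the selection of the phase I RP2D cohort is a fair criticism of an RP2D-only set, and the fix allows for it.

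**Conclusion.** The point holds as a gap in a stated primary analysis. The set in 10.2 combines assigned regimens, and no estimate at the RP2D or by dose level is planned. Under an assumed 20-point difference between levels, the rate is displaced by about 2 to 4 points in the usual two-level case and up to about 7 with three levels, given a full phase II. The direction cannot be known in advance. The all-treated and RP2D rates have the same expectation only if toxicity is the same at every level opened.

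This does not affect how the RP2D is chosen. A reader might also infer that the efficacy estimate should move to the same combined RP2D set. The documents do not support that: the precision stated in 10.1 for pCR rests on the 20 phase II patients, and nothing here shows a defect in it.

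The change should be made, but the trial's design does not depend on it.

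**What to change.** In 10.2:

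- Report adverse-event rates with exact 95% intervals by assigned dose level.
- Make the headline estimate the rate in all patients assigned the RP2D, meaning the phase I RP2D cohort plus phase II.
- Give the phase II patients alone as a sensitivity estimate, because the phase I RP2D cohort was selected for few first-cycle DLTs.
- Keep the all-treated rate as supportive.
- State that groups are defined by assigned dose, and describe within-patient reductions (allowed in 4.2 and 5.3) alongside.
- Align the synopsis sentence on all enrolled patients with the sets named in 10.2.

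Leave the set for pCR and downstaging as it is.

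The cost is wording, one extra table and a somewhat wider headline interval. At a rate near 30%, 8/26 gives 14.3% to 51.8% (37.5 points wide). The all-treated 10/32 gives 16.1% to 50.0% (33.9 points) in a two-level case, and 11/38 gives 15.4% to 45.9% (30.5 points) in the three-level maximum. No further patients or data are needed.
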